### Power for Secondary Outcomes

For Aim 3, we consulted our stakeholders to determine what would represent meaningful differences in healthcare utilization. Based on these discussions, we will categorize completed planned outpatient visits in “less than 50%,” “between 50 and 75%,” and “more than 75%.” Based on highly conservative estimates from data collected on patients who were eligible (based on insurance, geography and preference) and referred to Moss Rehab Hospital (one of our study sites), 4%, 17%, and 79% of the individuals received “less than 50%,” “between 50 and 75%,” and “more than 75%” of their scheduled physical therapy, occupational therapy, and speech therapy care visits (these data do not include other outpatient visits, such as mental health and primary care visits, that are known to have low adherence rates). Under the assumptions that our RDP group would have a proportion of 0.79 of people going to more than 75% of their scheduled visits, with a significance level of 0.05, power of 0.80, and varying the sample size from 500 to 900, we calculated the size of change in the proportion of people receiving 75%+ visits in the RTP group that we would be able to detect. We would be able to statistically detect a proportion of 0.88 in the RTP group with a sample size of 500 and a proportion of 0.86 with 900 (see graph below). Therefore, we would have enough power to detect a small change in proportions.

[figure not shown]
We will also test differences in number of hospitalizations, number of emergency department visits, and number of unplanned outpatient visits per year. These outcomes will be compared using a Poisson model. For the power analysis, we adjusted the significance level to 0.017 after using Bonferroni adjustment (0.05/3), and we considered sample sizes of 700, 800, and 900 (to assess the effect of attrition of roughly 10% and 20%). From our previous work, we only have rough estimates of the events of interest (0.42 hospitalizations per year from [name] et al. and 2.25 medical encounters of any type (not distinguished as planned or unplanned) per year from Salisbury et al.). Therefore, we considered the base rates of 1-5 events per year for the RDP group and calculated the power of detecting a decrease in that rate of 10%, 20%, 30%, and 40% in the RTP group. Using G\*Power and the specifications above, the summary of the findings are as follows:

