### **Power for Secondary Outcomes:**

For Aim 3, under the assumptions that our SDC group would have a proportion of 0.79 of people going to more than 75% of their scheduled visits, we calculated the size of change in the proportion of people receiving 75%+ visits in the OTC group that we would be able to detect with a significance level of 0.05 (two-tailed proportion test), power of 0.80, and varying the sample size from 100 to 900.

With 80% power, we would be able to statistically detect a proportion in the OTC group of 0.91 with a sample of 300 individuals, 0.88 with a sample size of 500, and of 0.86 with 900 (see graph below).

[figure not shown]
[figure not shown]
We will also test differences in number of hospitalizations, number of emergency department visits, and number of unplanned outpatient visits per year. These outcomes will be compared using a Poisson model. For the power analysis, we adjusted the significance level to 0.017 after using Bonferroni adjustment (0.05/3), and we considered sample sizes of 300, 500, 700, and 900. We considered the base rates of 1-4 events per year for the SDC group and calculated the power of detecting a decrease in that rate from 10% to 50% in the OTC group. Using G\*Power and the specifications above, the summary of the findings are as follows:

- The higher the base rate for the SDC group, the higher the power to find a difference;
- Power is at least 80% to find a decrease of 20% in the number of events, except when the base rate is 1, in which case the decrease would need to be 22-25% to be detected;
- Attrition or low enrollment (represented by sample sizes of 300, 500 and 700) have an effect but might be important only for a small base rate (such as 1 visit/year) and sample size 300 (unlikely to happen);
- Power for secondary analysis will be high to find a decrease of 20% in mean number of events (equivalent to odds ratio of .8 when comparing the OTC to the SDC group), except for sample lower than 500 (which is unlikely to happen).

The graphs below show the power for each base rate (odds ratio in x-axis and power in the y-axis).

[figure not shown]
[figure not shown]
Base rate = 1

Base rate = 2

[figure not shown]
Base rate = 3

Base Rate = 4

For Aim 4, for caregiver outcome, we assumed the following parameters:

- Sample sizes from 250 to 600 (by 50);
- Significance level of 0.05,
- SD=13 for both groups (based on the higher SD in Powell et al.),
- T-test (two-tailed)

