**Aim 1, Hypothesis 1:** Both the PART-O-17 and the QoLIBRI measures are numeric with a fairly large range that can be considered as continuous for data analysis. We will test the difference in means for PART-O-17 and QoLIBRI between the two groups at 6-month post-discharge using a two-sided t-test for independent samples. We will also test if the intervention has a long-term effect by comparing the two groups at 12-months post discharge using the same type of t-test.

**Aim 2, Hypothesis 2:** To compare the trajectory of improvement for 3-, 6-, 9- and 12-months post-discharge, we will plot individual trajectories over time and if it appears that the majority of people are leveling off over time we will consider a growth model. Otherwise, we will use a linear mixed model, with the outcome (PART-O-17 or QoLIBRI) as the response variable, and time and other factors (such as age, sex, race/ ethnicity, education, injury severity) as explanatory variables, and add intervention group and its interaction with time to test whether the interventions and time had an effect in the trajectory of the outcome.

**Aim 3, Hypothesis 3:** To compare the healthcare utilization in the first-year post discharge, the two groups will be compared on the distribution of categories of completed planned outpatients visits (less than 50%, between 50 and 75%, and more than 75%) by using a Chi-Square test. Both, the number of urgent care visits and the number of unplanned hospitalizations will be compared by means of a Poisson regression, which will include group and possibly adjusting for other factors (age, sex, race/ethnicity, education, injury severity). A statistically significant coefficient for intervention groups will show that the two groups differ in emergency and unplanned medical visits.

**Aim 4, Hypothesis 4a:** To compare caregiver burden, HRQOL, and satisfaction with roles and activities, we will apply t-tests for difference of means for independent samples for those measures that are found to have a normal distribution. We will also conduct heterogeneity of treatment effects analyses as we planned for other measures.

**Aim 4, Hypothesis 4b:** Using the Bakas Caregiving Outcomes Scale, Zarit Burden Interview, Sf-12, and the PROMIS Satisfaction with Social Roles and Activities for caregivers at 3-, 6-, 9- and 12-month follow-ups as response variables, we will fit a linear mixed model or growth model similar to the ones in hypothesis 2.

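### Aim 3 visit completion: the plan tests three categories (2 df), but the stated 80% power is for a two-proportion test of the top category, and the 0.86 figure assumes 900 analysed when 720 are expected

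*Combined protocol and SAP*

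**What the plan says.** **Analysis.** Under Aim 3, Hypothesis 3 in the Data Analysis Plan, "the two groups will be compared on the distribution of categories of completed planned outpatients visits", namely "less than 50%, between 50 and 75%, and more than 75%) by using a Chi-Square test". Two groups by three categories gives 2 degrees of freedom, and the order of the categories is not used. Hypothesis 3 itself is directional: RTP patients are expected to complete a higher share of their planned outpatient visits.

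**Power.** Power for Secondary Outcomes takes its base rates from one study site, where "4%, 17%, and 79% of the individuals received" care in the lowest, middle and highest categories. From there it uses the highest category only: it assumes that "our RDP group would have a proportion of 0.79 of people going to more than 75% of their scheduled visits" and solves for the detectable RTP proportion "with a significance level of 0.05, power of 0.80, and varying the sample size from 500 to 900". The January 2019 recalculation names the test: "with a significance level of 0.05 (two-tailed proportion test), power of 0.80, and varying the sample size from 100 to 900". It reports 0.91 with 300 patients, and "0.88 with a sample size of 500, and of 0.86 with 900". Neither section says how RTP patients would divide between the two lower categories.

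**Retention.** The Recruitment/Enrollment Assessment Timeline plans for 80% retention, 180 of 900 patients lost. The Milestone Schedule in Appendix 1 counts 720 patients as complete 12-month follow-up.

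**The concern.** The test that was powered is not the test that is planned. A 2-df test spends part of its sensitivity on a second contrast, between the two lower categories, which the directional hypothesis does not address. Separately, the most favourable figure reported, 0.86, needs all 900 patients to be analysed, while the plan expects 720.

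At stake is how the Aim 3 result is read. The power section concludes that a small change in proportions can be detected, and the general analysis approach claims adequate power for the other aims. A non-significant three-category result would be judged against a power statement made for a different test and a larger sample.

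**Working it through.** **Inputs.** RDP distribution 0.04/0.17/0.79; RTP top category 0.86; two-sided alpha 0.05; 1:1 allocation; N = 900, or 720 = 0.80 × 900. The RTP split of the remaining 0.14 is not in the documents, so it is an assumption here and is shown as a range.

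**1. The plan's own figures.** With n per arm and p̄ the mean of the two proportions,

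power = Φ{ [|p1 − p0|√n − 1.96√(2p̄(1 − p̄))] / √[p0(1 − p0) + p1(1 − p1)] }.

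For 0.79 against 0.86 with n = 450: (0.07 × 21.213 − 1.96 × 0.5374)/0.5351 = 0.807, so power is 79.0%. Solving for exactly 80% gives 0.861 at N = 900, 0.883 at 500 and 0.906 at 300. These round to the stated 0.86, 0.88 and 0.91, so the stated arithmetic reproduces.

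**2. Same test, 720 analysed.** With n = 360: (0.07 × 18.974 − 1.0532)/0.5351 = 0.514, so power is 69.6%. The proportion detectable with 80% power becomes 0.868.

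**3. The planned 2-df test.** Noncentral chi-square, critical value 5.991, noncentrality λ = N × Σ d²/(4p̄), where d is the difference and p̄ the mean in each category.

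- *Remainder split 4:17, as in the base data* (0.027/0.113/0.86): Σ d²/p̄ = 0.00533 + 0.02267 + 0.00594 = 0.03394, so λ = 7.64 at 900 and 6.11 at 720.
- *All change from the middle category* (0.04/0.10/0.86): Σ d²/p̄ = 0 + 0.03630 + 0.00594 = 0.04224, so λ = 9.50 and 7.60.
- *Lowest category falls to 1%* (0.01/0.13/0.86): Σ d²/p̄ = 0.03600 + 0.01067 + 0.00594 = 0.05261, so λ = 11.84 and 9.47.

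| Test and assumed RTP distribution | Power, N = 900 | Power, N = 720 |
|---|---|---|
| Two-proportion, 0.86 | 79.0% | 69.6% |
| 2 df, 4:17 split | 69.6% | 59.2% |
| 2 df, all from middle | 79.4% | 69.4% |
| 2 df, lowest category at 1% | 87.9% | 79.3% |

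Simulation with 200,000 replicates gave 69.9% and 59.5% for the 4:17 split and 79.9% and 69.9% for the all-from-middle split. For the lowest category at 1% it gave slightly more than the approximation, 89.9% and 81.2%.

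The 4:17 split is about the minimum over all splits. There λ equals that of the two-category comparison, so the second degree of freedom costs power and adds no signal. Over the whole range, 2-df power for 0.86 is below 80% when the RTP share in the lowest category lies between about 1.5% and 4.0% at N = 900, or between about 1.0% and 4.8% at N = 720.

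**4. Detectable proportion for the planned test.** Under the 4:17 split, 80% power needs an RTP proportion of 0.868 at N = 900 and 0.876 at N = 720. At 0.88 and N = 720, power is 83.8% for this test and 90.4% for the two-proportion test.

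**The case against.** Three stronger readings are tempting, and the documents do not support them.

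- *The planned test lacks 80% power.* A reader might infer this from the extra degree of freedom. But no RTP split is given, so the power of the 2-df test cannot be derived from the documents. If all the change comes from the middle category, nothing is lost at 900 (79.4% against 79.0%). If RTP mainly empties the lowest category, the 2-df test is the more powerful of the two.
- *The power section ignores attrition.* It applies no loss rate to this endpoint, but it varies N from 500 to 900, and in 2019 from 100 to 900, with results at 500 and 300. The expected 720 lies inside both ranges, and the graphs that may show it are not reproduced in the text available. Only the 0.86 figure requires all 900.
- *The figures are miscalculated.* They reproduce; the problem is that test and power do not match.

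It can also be said that 0.86 is a detectable value and not a design target, that the worst-case 0.876 at 720 rounds to the 0.88 already printed for 500, that the three categories came from stakeholder discussions, and that the plan promises caution and effect sizes for non-primary outcomes. All of this stands, and it limits the size of the point. It does not supply a power statement for the planned test.

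**Conclusion.** The mismatch is real and modest. The stated 80% belongs to a two-proportion comparison of the top category. No power is stated for the three-category chi-square. At 0.86 and 720 analysed, the two-proportion test has about 70%, and the planned test has 59% to 69% for splits from 4:17 to all-from-middle, rising to 79% if the lowest category falls to 1%. So at 720 the planned test is below 80% for 0.86 under most plausible splits, but not under all.

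In terms of what can be detected, the correction is about 1 to 2 percentage points: from 0.86 to 0.868 (two-proportion) or 0.876 (2 df, 4:17 split).

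These results rest on the plan's 0.04/0.17/0.79 base distribution, on 720 patients contributing to this outcome, and on the assumed splits. The plan itself notes that its base data leave out visit types with poor adherence, so the percentages should not be read as precise. Primary outcomes are unaffected.

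**What to change.** Choose one of two changes in the Aim 3 analysis text and align the power section with it.

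1. **Preferred:** make more than 75% against 75% or less the formal Aim 3 visit-completion test, using a two-proportion test and reporting the difference with a confidence interval. Show the three categories descriptively. Restate the detectable proportion at 720 evaluable as about 0.87. Changing the test alone does not restore 80% power at 0.86; the restated figure is needed as well.
2. **Alternative:** keep the three-category test, state the assumed RTP distribution over all three categories, and give 2-df power at 720. Under a 4:17 split the detectable proportion is about 0.876.

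Either costs a sentence or two of plan wording and one restated figure. Under the first option, shifts between the two lower categories leave the formal test, and power is lower than with three categories if RTP works mainly by emptying the lowest one (at 0.86 with that category at 1%: 79% against 88% at 900, and 70% against 79% at 720). The second option avoids that loss, but the test still ignores the direction of Hypothesis 3.

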- The higher the base rate for the RDP group, the higher the power to find a difference;
- Power is at least 80% to find a decrease of 20% in the number of events, except when the base rate is 1, in which case the decrease would need to be 22-25% to be detected;
- Attrition (represented by sample sizes of 800 and 700) have an effect but might be important only for a small base rate (such as 1 visit/year);
- Power for secondary analysis will be high to find a decrease of 20% in mean number of events (equivalent to odds ratio of .8 when comparing the RTP to the RDP group), even when sample size is depleted by attrition.

[figure not shown]
The analyses will be repeated adjusting for other factors (age, sex, race/ethnicity, education, injury severity, for example), to explore the effect of those factors on the outcomes (we are not powering the study for these analyses as they are exploratory in nature).

The graphs below show the power for each base rate (odds ratio in x-axis and power in the y-axis).

[figure not shown]

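### The claim of high power for a 20% fall in counts fails at 0.42 hospitalisations per year, the only annual hospitalisation rate cited, and the planned Poisson regression makes no provision for over-dispersion

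*Combined protocol and SAP*

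**What the plan says.** In the Data Analysis Plan, under Aim 3, Hypothesis 3, "Both, the number of urgent care visits and the number of unplanned hospitalizations will be compared by means of a Poisson regression". Covariates may be added, but this is left open. A significant group coefficient is to be taken as showing that the arms differ. The general approach sets alpha at 0.05 for all analyses, without multiplicity adjustment.

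The Power for Secondary Outcomes section lists hospitalisations, emergency department visits and unplanned outpatient visits as the counts, at alpha 0.017 (0.05/3). On event rates it says "we only have rough estimates of the events of interest (0.42 hospitalizations per year", alongside 2.25 medical encounters of any type per year. It continues: "Therefore, we considered the base rates of 1-5 events per year for the RDP group". Its findings are that "Power is at least 80% to find a decrease of 20% in the number of events, except when the base rate is 1", where a fall of 22-25% would be needed, and that attrition "might be important only for a small base rate (such as 1 visit/year", given as an example). The closing bullet calls power for a 20% fall high, "even when sample size is depleted by attrition".

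The January 2019 revisit repeats this on a shorter grid, "We considered the base rates of 1-4 events per year for the SDC group", and again concludes: "Power for secondary analysis will be high to find a decrease of 20% in mean number of events". The only exception there is for samples below 500.

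**The concern.** Hospitalisation is one of the two counts in Hypothesis 3, and the only annual rate given for it lies below the lowest rate at which power was calculated (1/0.42 = 2.4 times the cited rate). The closing statements carry no base-rate limit, so they read as covering hospitalisations. If they do not, a null hospitalisation result would be read as evidence of no effect when the comparison had roughly even odds of detecting a 20% fall.

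The second issue is the standard error. Poisson regression fixes the variance at the mean. If some patients are repeatedly admitted or repeatedly use urgent care, the variance exceeds the mean, intervals are too narrow and the false-positive rate exceeds 5%. Covariate adjustment removes the problem only as far as it absorbs the excess variance. Cautious interpretation, which the plan promises for non-primary outcomes, does not correct a standard error.

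**Working it through.** **Inputs.** Rate 0.42 per year, alpha 0.017 and n = 700 to 900 come from Power for Secondary Outcomes. Alpha 0.05 is from the general approach of the analysis plan. Allocation is 1:1. The 720 patients completing 12 months are in the Milestone Schedule (80% of 900). Assumptions: two-sided tests (not stated for the Poisson model) and one year of follow-up per person.

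**Formulas.** With r the RDP rate, RR = 0.8, n/2 per arm and dispersion phi (1 for pure Poisson):

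- Wald: SE² = phi × [1/(r·n/2) + 1/(0.8r·n/2)]; power = Φ(|ln 0.8|/SE − z), with |ln 0.8| = 0.2231.
- Signorini: power = Φ([√(n·r)·0.2231 − z·√4] / √4.5), where 4.5 = 2 + 2/0.8. This is the more favourable of the two.
- z = 1.960 at alpha 0.05 and 2.387 at alpha 0.017.

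**Reproducing the plan's figures (alpha 0.017, 20% fall).** At rate 2, power is 0.94-0.95 for n = 700 and 0.98-0.99 for n = 900. At rate 1 it is 0.65-0.70 for n = 700 and 0.78-0.82 for n = 900. By the Wald formula, the fall needed for 80% power at rate 1 is 20.4% (n = 900) to 23.0% (n = 700), slightly below the stated 22-25%. The plan's grid is therefore essentially confirmed.

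**At the cited rate of 0.42.** For n = 720, expected events are 360 × 0.42 = 151.2 and 360 × 0.336 = 120.96. SE = √(1/151.2 + 1/120.96) = 0.1220, and 0.2231/0.1220 = 1.829. Power is Φ(1.829 − 1.960) = 0.448 at alpha 0.05 and Φ(1.829 − 2.387) = 0.289 at alpha 0.017. For n = 900, SE = 0.1091, giving 0.534 and 0.366.

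| n | alpha | Wald | Signorini |
|---|---|---|---|
| 720 | 0.05 | 0.448 | 0.493 |
| 900 | 0.05 | 0.534 | 0.578 |
| 720 | 0.017 | 0.289 | 0.337 |
| 900 | 0.017 | 0.366 | 0.419 |

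A simulation of 200,000 trials agrees with the Wald column at alpha 0.05 (0.45 and 0.54).

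With n = 720, 80% power for a 20% fall needs 0.9-1.0 events per year at alpha 0.05, or 1.2-1.3 at 0.017. At 0.42 per year, the fall detectable with 80% power is 28-30% at 0.05 or 32-34% at 0.017.

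**Unplanned admissions only.** Hypothesis 3 concerns unplanned hospitalisations, and 0.42 is not stated to be limited to them. If 75% or 50% were unplanned (assumed shares), power at n = 720 and alpha 0.05 would be 0.35-0.40 or 0.25-0.29.

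**Over-dispersion.** With a Poisson standard error, type I error = 2(1 − Φ(1.96/√phi)), and the interval is 1/√phi of its proper width. The phi values are assumed.

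| phi | Type I error | Interval too narrow by |
|---|---|---|
| 1.1 | 6.2% | 5% |
| 1.3 | 8.6% | 12% |
| 1.6 | 12.1% | 21% |
| 2.0 | 16.6% | 29% |

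A simulation (20,000 trials, 360 per arm, mean 0.42, negative binomial counts) gave 8.0%, 12.3% and 16.6% with Poisson errors at phi 1.25, 1.6 and 2.0. Robust errors gave 5.0%, 5.2% and 5.2%. Under true Poisson counts with a 20% fall, power was 0.448 with Poisson errors and 0.449 with robust errors.

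**Illustration only.** The Background reports 28% rehospitalised in the first year of injury. If that and 0.42 per year described the same person-years, which the documents do not show, phi would be at least 1.25 (72% with no event, 14% with one, 14% with two). It would be 1.60 under a negative binomial. The false-positive rate would then be about 8-12%.

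**The case against.** The plan calls 0.42 a rough estimate and uses a grid instead of adopting it. The cited source is titled as a study of rehospitalisation over 10 years, so 0.42 may not be a first-year-post-discharge rate. That uncertainty stands, and 0.42 is treated here as an assumption. It is still the only annual hospitalisation rate given, and the outcome analysed is narrower.

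The plan does disclose that power rises with base rate, that rate 1 falls short for a 20% fall, and that attrition may matter at a small rate. A careful reader could infer that lower rates do worse. But a fall of 22-25% at rate 1 does not convey power near one half at 0.42, and the closing statements have no such limit.

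The dispersion values are assumed, and the 28% figure concerns people with traumatic injuries counted from injury. This is correct. The recommendation does not depend on them, because robust errors cost essentially nothing if the counts are Poisson.

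Further analysis detail may sit in the Manual of Procedures, which is not part of these documents. Naming Poisson regression does not exclude robust errors, so this is an omission, not a prescribed error.

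Finally, Version 15.0 (01-23-23) postdates the scheduled end of 12-month follow-up (10/31/2022), so restating power cannot change the sample size. It can still change how a null result is read, and the standard error can be settled before the analyses scheduled to finish on 7/15/2023.

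**Conclusion.** The concern holds. As a general claim, the high-power statement is wrong as written for hospitalisations. At 0.42 per year, power for a 20% fall is about one half at alpha 0.05 (0.45-0.58 for n = 720 to 900; the lower end is Wald and the upper end Signorini). At the power section's own alpha it is 0.29-0.42. These figures assume that 0.42 applies to the RDP arm over one year and that there is no over-dispersion; over-dispersion or a lower unplanned rate would reduce them. The statement does hold at rates of 2 or more, including at n = 500 (0.83-0.86 at rate 2, alpha 0.017).

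The analysis plan should also provide for over-dispersion. The nominal 5% level holds only if counts are Poisson given the model. The direction of the error under over-dispersion is certain; its size is not known from the documents. Because both counts are secondary outcomes, this should be corrected but does not threaten the primary analysis.

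**What to change.** - **Analysis.** Specify negative binomial regression, or Poisson regression with robust (sandwich) standard errors, for both urgent care visits and unplanned hospitalisations.
- **Power.** Add a row at 0.42 per year with 720 retained, giving the fall detectable with 80% power. By the Wald formula this is about 30% at alpha 0.05 or 34% at 0.017 under pure Poisson (28% or 32% by Signorini). It is 33% or 38% at an assumed dispersion of 1.25, and 37% or 42% at 1.6.
- **Wording.** Limit the high-power statement to rates of about 2 or more per year, which also covers the 500-patient threshold in the 2019 revisit. State whether 0.42 covers all hospitalisations or only unplanned ones.
- **Minor reconciliation.** The power section has three counts at 0.017, whereas the analysis has two at 0.05; give one list and one alpha. This mismatch makes the stated count power conservative. Completed planned visits are powered as a two-proportion comparison but analysed with a three-category chi-square test; align the two.

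The cost is analysis-plan wording and one extra power row, with no change to data collection. Intervals will be wider if over-dispersion is present, and the stated power will look less favourable. For a 20% fall at 0.42 per year, n = 720 and alpha 0.05, Wald power is 0.45 under pure Poisson, 0.37 at dispersion 1.25 and 0.30 at 1.6.
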